6.4.3. Disease-Related Events and/or Disease-Related Outcomes Not Qualifying as SAEs

6.4.4. Pregnancy

No Pregnant or Lactating Women will be eligible for this study,

Women with a negative pregnancy test within 7 days of enrollment and agree to use acceptable methods of birth control will be eligible for this study

6.4.5. Time Period and Frequency of Detecting AEs and SAEs

Investigators in writing must notify the NYPH-WCMC IRB as per Human Research Protection Policy in an immediate report within 7 working days of the occurrence of all serious or unexpected Adverse Events (AEs) in NYPH-WCMC research subjects, whether or not the events are considered study-related and within 24 hours of protocol deviations to eliminate hazards or breech of confidentiality

6.4.6. Prompt Reporting of Serious Adverse Events and Other Events to Novartis

Reporting to Novartis:

Any serious adverse events which occur during the clinical study or within 30 days of receiving the last dose of study medication, whether or not related to the study drug, must be reported by the investigator. In addition, any SAEs which occur as a result of protocol specific diagnostic procedures or interventions must also be reported.

All serious adverse events must be reported by facsimile within 24 hours to Novartis: [contact] .

The SAE report should comprise a full written summary, detailing relevant aspects of the adverse events in question. Where applicable, information from relevant hospital case records and autopsy reports should be included. Follow-up information should be forwarded to Novartis within 24 hours.

SAEs brought to the attention of the investigator at any time after cessation of eltrombopag and considered by the investigator to be related or possibly related to eltrombopag must be reported to Novartis if and when they occur. Additionally, in order to fulfill international reporting obligations, SAEs that are related to study participation (e.g., procedures, invasive tests, change from existing therapy) or are related to a concurrent medication will be collected and recorded from the time the subject consents to participate in the study until he/she is discharged.

6.4.6.1. Regulatory reporting requirements for SAEs

The PI and/or data coordinator will be reporting unexpected serious adverse events promptly to the IRB, FDA and to Novartis within appropriate regulatory timeframe.

We will be reporting:

- WCMC IRB as per WCMC AE Reporting Policy
- FDA as per Safety Reporting Requirements for IND and BA/BE (21CFR312.32)
- Novartis will be informed of all SAE within 24 hours
- WCMC Data Safety Monitoring Board

6.4.6.2 Data Safety Monitoring Plan:

We will be utilizing the Weill Cornell Medical College Data Safety Monitoring Board (DSMB) to review the IRB-approved protocol, informed consent forms and safety reports. The DSMB will review data semi-annually to evaluate the safety, efficacy, and compliance with all local IRB, FDA and ICH regulations/requirements for this study. Adverse events and unanticipated problems will be submitted to the DSMB semi-annually. A Grade 4 or above adverse event will result in an immediate submission of a periodic report to the DSMB. All serious adverse events will be immediately submitted to Novartis and to the FDA under the IND.

The Principal Investigator will submit all written DSMB recommendations at the time of the continuing review. Individual recommendations will be submitted upon receipt of review comments.

Safety Evaluation

This protocol is investigator initiated. The Principal Investigator is responsible for the study and will monitor the safety of the patients on the protocol.

The following safety will be reviewed by the Principal Investigator:

- Physical Exam
- Vital Signs
- Laboratory results (blood count, liver function tests, reticulocyte count)
- SAE and AE events
- Bone marrow aspirations/biopsies (if relevant)

Early Stopping Rules

Individual Stopping Rules

- Adverse event that would in the investigators judgment, make continued participation in the study an unacceptable risk
- Development or diagnosis of new thrombotic event

- Development of new-onset, clinically-significant, ocular changes related to cataracts on serial ophthalmology examinations
- Development of MF3 fibrosis on bone marrow examinations
- Development of Drug Induced Liver Injury

Liver chemistry stopping criteria and follow up requirements have been implemented to assure subject safety and evaluate liver event etiology in alignment with the FDA Guidance for Industry – Drug-Induced Liver Injury: Premarketing Clinical Evaluation.

Liver chemistry stopping criteria 1-5 are defined as follows:

1. ALT $>3x$ ULN and bilirubin $>2x$ ULN ($>35\%$ direct bilirubin) (or ALT $>3x$ ULN and INR > 1.5 , if INR measured and prolongation not related to another medication known to prolong INR)

NOTE: If serum bilirubin fractionation is not immediately available, study drug should be discontinued if ALT $>3x$ ULN and bilirubin $> 2x$ ULN. Serum bilirubin fractionation should be performed if testing is available. If testing is unavailable, record presence of detectable urinary bilirubin on dipstick, indicating direct bilirubin elevations and suggesting liver injury.

2. ALT $\geq 5x$ ULN

3. ALT $\geq 3x$ ULN if associated with symptoms (new or worsening) believed to be related to hepatitis (such as fatigue, nausea, vomiting, right upper quadrant pain or tenderness, or jaundice) or believed to be related to hypersensitivity (such as fever, rash or eosinophilia).

4. ALT $\geq 3x$ ULN persists for ≥ 4 weeks

5. ALT $\geq 3x$ ULN and cannot be monitored weekly for 4 weeks

When any of the liver chemistry stopping criteria 1 - 5 is met, do the following:

- Immediately discontinue study treatment
- Report the event to Novartis and DSMB within 24 hours of learning its occurrence
- All events of ALT $> 3x$ ULN and bilirubin $>2x$ ULN ($>35\%$ direct bilirubin) (or ALT $>3x$ ULN and INR > 1.5 , if INR measured; INR measurement is not required and the threshold value stated will not apply to subjects receiving anticoagulants), termed 'Hy's Law', must be reported as an SAE (excluding studies of hepatic impairment or cirrhosis).
- NOTE: if serum bilirubin fractionation is not immediately available, study treatment should be discontinued if ALT $>3x$ ULN and bilirubin $>2x$ ULN. Serum bilirubin fractionation should be performed if testing is available. If testing is unavailable, record presence of detectable urinary bilirubin on dipstick, indicating direct bilirubin elevations and suggesting liver injury.
- Perform liver event follow up assessments, and monitor the subject until liver chemistries resolve, stabilize, or return to baseline values as described below

- Do not rechallenge with investigational product.

In addition, for subjects meeting liver stopping criterion 1:

- Make every reasonable attempt to have subjects return to clinic within 24 hours for repeat liver chemistries, liver event follow up assessments (refer to Section 0), and close monitoring
- A specialist or hepatology consultation is recommended
- Monitor subjects twice weekly until liver chemistries (ALT, AST, alkaline phosphatase, bilirubin) resolve, stabilize or return to within baseline values.

For subjects meeting any of the criteria 2 – 5:

- Make every reasonable attempt to have subjects return to clinic within 24-72 hrs for repeat liver chemistries and liver event follow up assessments
- Monitor subjects weekly until liver chemistries (ALT, AST, alkaline phosphatase, bilirubin) resolve, stabilize or return to within baseline values; subjects meeting criterion 5 should be monitored as frequently as possible

Liver Event Follow Up Assessments

For subjects meeting any of the liver chemistry stopping criteria 1 – 5, make every attempt to carry out the liver event follow up assessments described below:

- Viral hepatitis serology including:
 - Hepatitis A IgM antibody
 - Hepatitis B surface antigen and Hepatitis B Core Antibody (IgM)
 - Hepatitis C RNA
 - Cytomegalovirus by PCR
 - Epstein-Barr virus by PCR
- Hepatitis E IgM antibody
- Serum creatine phosphokinase (CPK) and lactate dehydrogenase (LDH).
- Fractionate bilirubin, if total bilirubin $>2x$ ULN.
- Obtain complete blood count with differential to assess eosinophilia.
- Record the appearance or worsening of clinical symptoms of hepatitis, or hypersensitivity, such as fatigue, nausea, vomiting, right upper quadrant pain or tenderness, fever, rash or eosinophilia as relevant on the AE form.
- Record use of concomitant medications, acetaminophen, herbal remedies, other over the counter medications, or putative hepatotoxins, on the concomitant medications form.
- Record alcohol use on the liver event alcohol intake form.

The following assessments are required for subjects with $ALT >3x$ ULN and bilirubin $>2x$ ULN ($>35\%$ direct) but are optional for other abnormal liver chemistries:

- Anti-nuclear antibody, anti-smooth muscle antibody, and Type 1 anti-liver kidney microsomal antibodies
- Liver imaging (ultrasound, magnetic resonance, or computerized tomography) to evaluate liver disease.

Liver Chemistry Monitoring Criteria

For subjects with $ALT >3x$ ULN but $<5x$ ULN and bilirubin $<2x$ ULN, without hepatitis symptoms or rash, and who can be monitored weekly for 4 weeks, the following actions

should be taken:

- Notify Novartis and DSMB within 24 hours of learning of the abnormality to discuss subject safety
- Can continue study treatment
- Must return weekly for repeat liver chemistries (ALT, AST, alkaline phosphatase, bilirubin) until they resolve, stabilize or return to within baseline values
- If at any time the subject meets any of the liver chemistry stopping criteria 1 – 5, proceed as described above
- If, after 4 weeks of monitoring, ALT <3x ULN and bilirubin <2x ULN, monitor subjects twice monthly until liver chemistries normalize or return to within baseline values.

Protocol Stopping Rules

Novartis and the Principle Investigator may terminate the study at any time. Early termination may occur due to emergent risk information or the decision by Novartis to discontinue the development of Eltrombopag.

Dose Escalation Rules

In Part 1 of the study, subjects will be randomly allocated at a two to one ratio to receive active treatment or placebo. All subjects in the study will receive 75 mg eltrombopag and then be randomized to receive either an additional 25 mg of eltrombopag or matching placebo tablet dispensed by the research pharmacy.

Eltrombopag will be administered bi-weekly for 8 weeks. If platelet count does not exceed 100,000, the additional eltrombopag or matching placebo tablet will be increased by 25 mg until the patient receives 75 mg eltrombopag and 75 mg eltrombopag or matching placebo (100mg x 2 weeks, 125 mg x 2 weeks, 150 x 4 weeks). If the patient's platelet count exceeds 100,000 during part 1 dosing will stop, subject will be considered a responder, and the subject will eligible for entering Part 2 (the long term treatment part of the study).

Dose modification during the long term extension portion of the trial will be made on the basis of individual platelet response to as high a dose as 150mg. If the platelet count is > 150,000 ul and < 400,00 ul the daily dose will be adjusted and if > 400,000 ul the medication will be held and monitor will be as per the prescribing information for eltrombopag in the package insert. However, if the P-I determines that adjusting or stopping the subject's dose will negatively affect the subject, he or she may decide not to escalate, reduce, or stop the subject's dose. Circumstances in which this may occur include, but are not limited to: investigator is tapering other medications or the subject has a viral infection. Viral infections have been known to both increase and decrease platelet count in patients with ITP. It is suggested that the increased presence of inflammatory molecules during a viral infection increases platelet production, causing platelet count to increase. Alternatively, platelet count may decrease by virtue of activating the reticuloendothelial system causing greater phagocytosis of antibody-coated platelets and/or platelet production.

Data Collection and Monitoring

Data will be collected and entered into a Microsoft excel eCRF by the clinical research coordinator. Data will be entered into the eCRF after each study visit. The Principal investigator will verify the data quarterly to ensure that the data collected and entered is accurate.

Interim Analysis:

An interim analysis was performed after 18 patients were enrolled in the study. The data suggested that non-splenectomized patients tended to have higher average platelet counts compared to splenectomized patients for the first 8 weeks in the open-label extension phase. When subjects were on active drug, the results revealed that males tended to have a higher complete response rate compared to females. Of note, three subjects were removed due to SAEs, however only one patient was removed because of a study drug related event (elevated LFTs). Further analysis will be performed to evaluate the long term efficacy and safety of Eltrombopag at doses higher than 75 mg after 36 and then 60 patients have completed 8 weeks of active medication.

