Dose escalation will continue, despite satisfaction of the primary endpoint of study ($> 50,000$ and $> 20,000$ above baseline), until the platelet count reaches 100,000. The rationale for this approach is to maximize clinically relevant responses for the subjects and standardize data for analysis. Subjects will stop study medication if the platelet count is within the normal range, thereby minimizing any safety risk associated with elevated platelet count. By continuing to dose escalate subjects until the platelet count is $> 100,000$, the maximum response and correlation of dose will be tracked allowing better understanding of sustained response and dose-dependent response, which can be applied to future consideration dosage for periods of short-term hemostasis (i.e surgical procedures). The 8 weeks of data collected in enrolled subjects on the standardized

protocol will have the balance of consistency of dosage and unequivocality of response while maintaining subject safety.

If agreed on by the P-I, subjects may obtain local counts or see their local hematologist for study visits. All study-required procedures will be faxed to the P-I for review. The appropriate dosing adjustments will be determined by the P-I.

According to the new consensus guidelines (Provan Blood, 2009), male and female subjects with > 1 year duration of ITP are diagnosed with chronic ITP. Enrollment began with adult subjects \geq 18 years of age, and was extended to include pediatric patients $>$ 12 years of age after a review of this unblinded safety information by the independent Data Safety Monitoring Officer (DSMO). Additionally, we will now allow the inclusion of pediatric patients \geq 3 year of age to enroll on the protocol. The rationale for treating patients on this study is to allow people to be successfully treated and thus increase their platelet count by using a higher dose of eltrombopag when they do not respond to 75 mg daily of eltrombopag. Since some children do not respond to 75mg, the rationale and the dosing (when and how to increase) would be the same.

Long Term Treatment Extension (Part 2): (48 months)

After 8 weeks or once dosing is stopped because the platelet count is $>100,000$, the subject will be unblinded, once the data forms are complete with the assistance of the research pharmacy.

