Subjects who received and responded to eltrombopag higher dose treatment will have the option to continue therapy with periodic monitoring and ongoing dose adjustment on the open-label extension study.

Subject who had a platelet count $> 100,000$ can enter Part 2 at the dose at which the subject met primary response criteria after the platelet count decreases to $< 100,000$ /uL on serial monitoring in the immediate post-study monitoring period.

Subjects randomized to the placebo group who did not respond will have the opportunity to receive open label escalated dose eltrombopag over 8 weeks following the study protocol as if they had been randomized to active drug in the study. This group will provide the “confirmatory group” to see if the rate of response in the randomized group can be confirmed in this group.

Consent will be obtained for additional monitoring with bone marrow aspirate and biopsy at 1 year (at year 2, year 3, year 4) and additional ophthalmologic examinations for cataracts at 6 months and 18 months.

It is considered standard of care to monitor all patients as possible who have been on eltrombopag treatment for 1 year because of the higher doses of eltrombopag administered in this protocol. All subjects will have bone marrow aspiration/biopsies for their clinical care, no bone marrows will be performed for research purposes only.

Optional PK sampling will be done 4 weeks after the subject has been on active study drug (or at another time point if this is not convenient). There will be 3 samples drawn: the 1st sample will be drawn prior to taking the study drug for that day, the 2nd PK sample will be drawn 2-4 hours after the dose was taken and the 3rd sample will be drawn 5-8 hours after the dose was taken. These PK tests are being done to measure how much eltrombopag is in the blood at various time points following administration of eltrombopag and can be compared to published data.

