At Enrollment: (Part 1)

CBC with Differential
Reticulocyte Count
Peripheral Smear
CMP (Sodium, Potassium, Bicarbonate, Chloride, BUN, Creatinine, Glucose, Calcium, Total Protein, Albumin, including AST/ALT, Fractionated Bilirubin Level)
Platelet Reticulocyte Count
Eye Examination for caratacts
History, Physical with Vital Signs and Bleeding Score
HRQOL

Every 2 Weeks until week 8:

Reticulocyte count, Platelet Reticulocyte count
Peripheral Smear (if indicated)
CMP
History, Physical with Vital Signs and Bleeding Score

Long Term Treatment Extension: (Part 2)

Performed at each study visit:

CBC with Differential platelet count, Reticulocyte count, Platelet Reticulocyte count
Peripheral Smear (if indicated)
History, Physical with Vital Signs

After the end of treatment during the dose escalation phase, all subjects can be monitored at 4 weeks intervals and then can go to every 8 weeks for the remainder of the study at the discretion of the investigator (investigator may require subjects to come in for additional monitoring if deemed necessary).

After 6 months on therapy:

Eye Examination

After 12 months on therapy:

Bone Marrow Aspirate and Biopsy
HRQOL

After 18 months on therapy:

Eye Examination

After 24 months on therapy

Bone Marrow Aspirate and Biopsy

*Please Note: A bone marrow aspiration/biopsy will only be performed at 24 months if the subject's reticulin fibrosis grade is a 2 or 3 during the 12 month procedure.
HRQOL

After 36 Months on therapy

Bone Marrow Aspirate and Biopsy

*Please Note: A bone marrow aspiration/biopsy will only be performed at 36 months if the subject's reticulin fibrosis grade is a 2 or 3 during the 24 month procedure.

HRQOL

After 48 Months on therapy

Bone Marrow Aspirate and Biopsy

*Please Note: A bone marrow aspiration/biopsy will only be performed at 48 months if the subject's reticulin fibrosis grade is a 2 or 3 during the 36 month procedure.

HRQOL

Post Study Period after completion of dosing

Weekly

CBC with Differential platelet count, Reticulocyte count, Platelet Reticulocyte count
Peripheral Smear (if indicated)

History, Physical with Vital Signs and Bleeding Score
HRQOL (Week 1 – End of 8 Week Blinded study/ End of Extension Study)

Every 2 Weeks until week 4:
CMP
History, Physical with Vital Signs and Bleeding Score

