4. SUBJECT SELECTION AND WITHDRAWAL CRITERIA

4.1. Number of Subjects:

60 subjects will be enrolled.

4.2. Inclusion Criteria:

Subject or their parent/ guardian has signed and dated a written informed consent

Males and Females aged 3 year or older, who can swallow a tablet, and are diagnosed with chronic ITP according to the new consensus guidelines (Provan, Blood, 2009) are eligible.

No indication of a disease which may cause thrombocytopenia other than ITP---- no specific testing required

Subjects with thrombocytopenia $\leq 50,000 /uL$ after at least 21 days of daily dosage with eltrombopag 75mg

Stable dosage of concomitant treatments for ITP
 ≥ 2 weeks or longer (corticosteroids);

At least 2 weeks from rescue therapy for ITP (WinRho, IVIG, corticosteroids, platelet transfusion) or 1 week if therapy has clearly been ineffective

At least 4 weeks from rituximab treatment

Pregnant or Lactating Women are excluded

Women of child-bearing age with a negative pregnancy test within 7 days of enrollment and who agree to use acceptable methods of birth control will be eligible for this study

Female subjects or female partners of male subjects must either be of non-child bearing potential (hysterectomy, bilateral oophorectomy , bilateral tubal ligation or post menopausal for more than one year) OR, if of child bearing potential, using one of the following highly effective methods of contraception.
-complete abstinence from intercourse

- Intrauterine device (IUD)
- Two forms of barrier contraception. diaphragm plus spermicide, or for males condoms plus spermicide.
- Male partner is sterile and is the only partner of the female.
- Systemic contraceptives

4.3. Exclusion Criteria:

Previous history of eltrombopag-related LFT elevation that required sustained interruption of treatment

Previous history of immediate or delayed hypersensitivity reaction or idiosyncrasy to drugs chemically related to eltrombopag

Known HIV Infection

History of Arterial or Venous Thrombosis within the past year or requiring ongoing therapy

Known Active Hepatitis C infection

Elevated AST/ALT or Creatinine > 1.5 times upper limit of normal in 4 weeks prior to enrollment*

Abnormalities in WBC, ANC and Hemoglobin > 1.5 times upper or lower limit of normal*

* Subjects can be rescreened to be included

4.4. Withdrawal Criteria:

Subject may withdraw consent at any time

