6.1. Critical Baseline Assessments

Screening to ensure subject eligibility criteria will occur within 30 days prior to administration of study medication. Screening assessments will include CBC, CMP (Sodium, Potassium, Bicarbonate, Chloride, BUN, Creatinine, Glucose, Calcium, Total Protein, Albumin, including AST/ALT, Fractionated Bilirubin Level), D-Dimer and urine pregnancy test (for women of childbearing potential).

6.2. If subject meet all other criteria for enrollment, a baseline ophthalmologic examination will be performed within 2 weeks of administration of study medication.

6.3. Primary Response Criteria:

Complete Response (CR) will be defined as a 2 consecutive platelet counts $\geq 50,000 / \mu\text{L}$ AND $> 20,000$ more than the baseline platelet count at enrollment within the 8 week increased dose window not as a result of rescue treatment. Partial Response (PR) will be defined as a 2 consecutive platelet counts $\geq 50,000 / \mu\text{L}$ OR $> 20,000$ more than the baseline platelet count at enrollment within the 8 week increased dose window not as a result of rescue treatment.

For uniformity of dosing and data analysis and for better understanding of increased dose effects, patients randomized to the treatment arm will automatically take:

- 100 mg for 2 weeks
- 125 mg for 2 weeks
- 150 mg for 4 weeks

However, if the platelet count increases to $\geq 100,000 / \mu\text{L}$, study drug will be interrupted and will not be resumed until platelet count is below 100,000 / μL and the patient desires to enroll on the Part 2 long term treatment extension study. The patient will finish with the Part 1 of the study at this point but can enter Part 2 the long term treatment extension study at dose at which the patient met primary response criteria, after the platelet count decreases to $< 100,000 / \mu\text{L}$ on serial immediate post-study monitoring period.

Rescue treatment will be defined as new treatment for chronic ITP eg IV anti-D or IVIG, an increased dose of steroids, or platelet transfusion. Use of rescue treatments will be allowed, but patients will be regarded as non-responders for the duration of rescue treatment and until 2 weeks beyond.

Secondary Response Criteria:

-Platelet Count $\geq 50,000$ and $> 20,000$ above baseline for at least 3 of the last 4 of 8 weeks independent of rescue therapy

- Platelet Count \geq 50,000 /uL and $>$ 20,000 above baseline for any 4 of 8 weeks independent of rescue therapy

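### Part 1 dose increases at Weeks 2 and 4 depend on platelet count alone, so by default they go ahead during a liver watch (ALT 3 to <5 x ULN)

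*Combined protocol and SAP*

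**What the plan says.** **Escalation.** The Dose Escalation Rules (under 6.4.6.2) tie each Part 1 step to the platelet count: "If platelet count does not exceed 100,000, the additional eltrombopag or matching placebo tablet will be increased by 25 mg". Section 6.3 says that "patients randomized to the treatment arm will automatically take" 100 mg for 2 weeks, 125 mg for 2 weeks and 150 mg for 4 weeks. Section 3.1 adds: "Dose escalation will continue, despite satisfaction of the primary endpoint of study", with 100,000 as the end point.

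**Who is covered.** For children from 3 years, Section 3.1 says "the rationale and the dosing (when and how to increase) would be the same". Placebo non-responders may take the escalation open label, "following the study protocol as if they had been randomized to active drug in the study".

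**Liver watch.** Sections 6.4.1 and 6.4.6.2 define a monitoring band: ALT 3 to <5 x ULN, bilirubin <2 x ULN, no hepatitis symptoms or rash, and weekly follow-up feasible for 4 weeks. In that band the subject may remain on treatment, has weekly chemistries, and is reported within 24 hours for a safety discussion (to the company in 6.4.1; to the company and the DSMB in 6.4.6.2). Dose level is not mentioned.

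**Overrides.** The liver stopping criteria and the investigator's power to withdraw a subject at unacceptable risk take precedence over any step. Express discretion not to escalate is written for the long-term extension (3.1 and 6.4.6.2). Section 3.1 also says "The appropriate dosing adjustments will be determined by the P-I", in the paragraph on local counts and local visits.

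**The concern.** Section 6.4 says the drug may cause hepatotoxicity and reports liver test abnormalities in 11% of eltrombopag patients and 7% of placebo patients in controlled ITP studies. This trial goes above the approved 75 mg maximum. A subject being watched for possible liver injury would, under the written rule, move further above that maximum because the platelet count is still low.

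One of the stopping criteria is ALT of at least 3 x ULN persisting for 4 weeks or more. The plan can therefore raise the dose during the very weeks in which it is waiting to see whether the rise persists.

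There is also a reporting consequence. If a step falls inside the watch, the dose at ALT onset differs from the later dose, so a by-dose reading of liver safety needs the dose at onset.

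**Working it through.** **Inputs.** Dose calendar (6.3 and Dose Escalation Rules): Days 1–14 100 mg, Days 15–28 125 mg, Days 29–56 150 mg. Watch: 4 weeks = 28 days. Chemistry panel in Part 1: "Every 2 Weeks until week 8" in 3.1; Appendix 1 shows Day 1 and Weeks 2, 4, 6 and 8. Turnaround time for the panel is not given, so both orders (result before or after the visit's step) are shown.

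**The plan's own calendar.** 2 + 2 + 4 = 8 weeks and 75 + 3 x 25 = 150 mg, as stated. After the Day 1 start, the increases are at Week 2 (Day 15) and Week 4 (Day 29).

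**Method.** For a result known on day d, the watch is days d to d + 27. Count the scheduled increases inside it, and compare the scheduled milligrams with 28 days at the dose current when the result is known. The figures are for active drug. They assume that the subject stays in the band and on drug for all 28 days and that the platelet count never exceeds 100,000.

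| Result known | Watch | As scheduled (mg) | Held (mg) | Difference | Week 2/4 steps inside |
|---|---|---|---|---|---|
| Day 1, after first dose | Days 1–28 | 14x100 + 14x125 = 3,150 | 28x100 = 2,800 | +350 (12.5%) | 1 (Week 4 step is on Day 29, the closing boundary) |
| Day 8, unscheduled test | Days 8–35 | 7x100 + 14x125 + 7x150 = 3,500 | 28x100 = 2,800 | +700 (25.0%) | 2 |
| Week 2, before the step | Days 15–42 | 14x125 + 14x150 = 3,850 | 28x100 = 2,800 | +1,050 (37.5%) | 2 |
| Week 2, after the step | Days 15–42 | 3,850 | 28x125 = 3,500 | +350 (10.0%) | 1 |
| Week 4, before the step | Days 29–56 | 28x150 = 4,200 | 28x125 = 3,500 | +700 (20.0%) | 1 |
| Week 4, after the step | Days 29–56 | 4,200 | 28x150 = 4,200 | 0 | 0 |
| Week 6 or Week 8 | – | already at 150 mg | 150 mg | 0 | 0 |

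**Day 1, before the first dose.** Counting the opening move from 75 to 100 mg as a step, holding 75 mg gives 28 x 75 = 2,100 mg against 3,150 mg: +1,050 mg, or 50%. This row is doubtful. Section 4.3 excludes "Elevated AST/ALT or Creatinine > 1.5 times upper limit of normal in 4 weeks prior to enrollment", so such a result may be mainly an eligibility question. The point is not closed, because 3.1 also lets subjects enroll and then take 75 mg for at least 3 weeks before Day 1.

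**The case against.** The strongest reply is that the plan is not silent. Part 1 treatment is a fixed titration, so permission to continue treatment naturally means continuing that titration. What is left is disagreement with a design choice. Control also exists case by case: a safety contact within 24 hours, weekly chemistries, mandatory stops (ALT of 5 x ULN or more, symptoms, raised bilirubin or INR, persistence, or weekly monitoring impossible), and investigator withdrawal. The number affected is unknown, extra milligrams are not an estimate of harm, and the placebo arm gets no extra drug in Part 1.

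Much of this stands. Escalation is indeed the stated default, and that is the difficulty: it has no liver exception. The 24-hour contact prompts a discussion but does not say what happens to a step due meanwhile. The dosing-adjustment sentence in 3.1 can be read to allow a hold for subjects seen locally. It gives no ALT criterion and does not clearly reach subjects seen at the centre.

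A reader might infer more than the documents support:

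- That a typical flagged subject takes one step. The documents give no distribution of ALT onset, and under the result-after-dosing order three of the five scheduled panels (Weeks 4, 6 and 8) give none.
- That one percentage in the table is the maximum. The figure depends on the dose taken as the held dose, as the Day 1 case shows.
- That the interim report (8.3.1.1) of one removal for drug-related elevated LFTs is an instance. The dose and ALT band are not given, so it shows relevance only.
- That no liver algorithm exists. Section 8.3.1.2 cites one for continuing or stopping drug. It is not in the supplied text and could not be checked.

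**Conclusion.** The point holds as a safety default worth changing. In Part 1 and in the open-label escalation, the Week 2 and Week 4 increases depend on platelet count with no exception for the liver monitoring band. Up to two 25 mg steps can fall inside the 4-week watch if the rise is known before the Week 2 step, one if it is found after that step and before the Week 4 step, and none afterwards. The milligram differences rest on 28 full days in the band and on drug; earlier resolution or a stop makes them smaller.

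The documents give no rate for this ALT band above 75 mg, so no count of affected subjects can be offered. The primary analysis and sample size are not touched. It would be wrong to conclude that the plan leaves these subjects unprotected or forces escalation regardless of liver findings, since the stopping criteria and investigator withdrawal override every step.

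**What to change.** Add to the Dose Escalation Rules and to 6.3: *Once a subject is known to be in the liver monitoring band, the current blinded dose level is held in both arms until ALT is <3 x ULN, or until the investigator, after the required notification, documents a decision to proceed.* Holding both arms preserves the blind.

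Apply the same hold to the open-label escalation of placebo non-responders. State that held subjects stay in the intention-to-treat analysis, that the 8-week window is not extended, and that dose of response uses the dose actually taken. List liver events by dose at onset. If the algorithm cited in 8.3.1.2 already contains a hold, cross-refer to it in both places instead.

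The cost is one sentence in two places, a line for the open-label escalation and a column in the liver listing. No tests are added, because panels are already scheduled at Weeks 2 and 4. There are two downsides. A few flagged subjects would reach 150 mg later or not at all, a small departure from the uniform titration that 6.3 wants. A pending panel result may also delay a step and separate dispensing from the visit.
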